### 9.3 POPULATIONS FOR ANALYSES

Three analysis populations will be defined and used in the statistical analyses: (1) a safety population, (2) a modified intent-to-treat (mITT) population, and (3) a per-protocol (PP) population.

Safety analyses will evaluate all randomized participants who received at least 1 dose of study drug and attended a post-baseline visit. Results will be presented based on the treatment received.

The primary statistical analyses will evaluate the mITT population, defined as all randomized participants who received at least 1 dose of study drug and had conjunctival hyperemia evaluated at both the Day 1 and Day 28 visits. Results will be presented based on the treatment assigned during randomization.

As a sensitivity analysis, the primary efficacy endpoint of conjunctival hyperemia will also be evaluated in the PP population of participants, who had no major protocol violations. Nominal data will be analyzed using the Pearson chi-square test or Fisher exact test. Conjunctival hyperemia, pterygium vascularity, BCVA, ophthalmoscopy, AS-OCT, and IOP data will be analyzed using analysis of variance models with dose strength as main effects. The analysis will be based on observed data. Missing values will not be imputed.

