### 1.3 SCHEDULE OF ACTIVITIES

Procedures	Screening Day -14 to -2 (SCR)	Enrollment/ Baseline Visit 1, Day 1 (V1D1)	Study Visit 2 Day 7 ±3 days (V2D7) ☎*	Study Visit 3 Day 28 ±3 days (V3D28)	Study Visit 4 Day 56 ±5 days (V4D56)	Final Study Visit 5 Day 84 ±5 days (V5D84)
Informed consent	X					
Demographics	X					
Medical, smoking, alcohol and drug history a	X					
Concomitant medication	X	X	X	X	X	X
Compliance assessment b			X*	X		
Concurrent procedures	X	X	X	X	X	X
Participant questionnaire c		X c	X	X c	X	X
Physical characteristics k	X			X		X
Vital signs d	X	X	X*	X	X	X
Hematology	X		X*	X		X
Serum chemistry	X		X*	X		X
Urinalysis	X		X*	X		X
Urine pregnancy test e	X	X		X		X
ECG (12-lead)	X	X		X		X
BCVA	OU	OU	OU*	OU	OU	OU
Ocular photography f	OU	SE	SE*	SE	SE	
AS-OCT g		SE	SE*	SE	SE	
IOP	OU	OU	OU*	OU	OU	OU
Biomicroscopy	OU	OU	OU*	OU	OU	OU
TFBUT		OU		OU	OU	OU h
Lissamine green staining		OU		OU	OU	OU h
Ophthalmoscopy	OU	OU		OU		OU
Plasma drug monitoring i		X		X	X i	
Randomization		X				
Study drug j		X		X		
AE review and evaluation		X l	X	X	X	X

\* Study Visit 2 (V2D7) is a phone call follow-up but may be conducted as an optional in-clinic visit at the discretion of the Principal Investigator. Asterisked assessments will only be conducted during in-clinic visit

- a) Medical history will include history of sun exposure
- b) On Day 7, study drug bottle will be weighed and returned if the visit is conducted in-clinic. If the visit is via phone, participants will be verbally instructed to maintain compliance and use the provided diary. On Day 28, study drug will be collected after administration of last dose and study drug bottles will be weighed
- c) Participant questionnaire will be administered prior to study drug administration at Visits 1 & 28
- d) Blood pressure, pulse, temperature, and breathing rate
- e) Females of childbearing potential only
- f) Ocular photography will be submitted to central reading center for assessment of conjunctival hyperemia, pterygium vascularity and pterygium vessel length
- g) At selected sites, AS-OCT imaging will be performed and submitted to central reading center for assessment of pterygium volume
- h) Test is optional at Day 84; to be performed if test shows abnormal findings at Day 56

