#### 9.4.4 SAFETY ANALYSES

All safety analyses will be conducted on the safety population using the following safety variables:

- Adverse events
- Concomitant medications
- Concurrent procedures
- Vital signs
- Laboratory tests (urinalysis, hematology, and serum chemistry parameters)
- Electrocardiogram
- Best-corrected visual acuity
- Intraocular pressure using a Goldmann applanation tonometer
- Biomicroscopy
- Tear film break-up time
- Lissamine green conjunctival staining
- Ophthalmoscopy

The Medical Dictionary for Regulatory Activities (MedDRA) nomenclature will be used to code AEs. For each AE reported, the number and percent of participants will be tabulated based on the preferred term. The tables will be generated by relationship to treatment as well as by system organ class and severity. Treatment-emergent AEs will be considered, as will AEs occurring prior to first dose and post-treatment.

---

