1.1 Changes from Protocol

Please refer to Section 10.4 PROTOCOL AMENDMENT HISTORY of protocol V3.0 for all amended contents. The following content are those may affect statistical analysis plan. The SAP and TFL shells have been amended accordingly:

Section	Contents (italic are added contents)
Study Objective	
 Evaluate the dose response of AG-86893 on pterygium vascularity, volume and vessel length (exploratory)
Study Visit	There will be 6 possible clinic visits, including a 14-day screening period (from Day -14 to -2), followed by a in-clinic treatment/observation period (Day 1, Day 7 [may be conducted as a phone follow-up], and Day 28), and 2 post-treatment follow-up visits for safety monitoring (Day 56 and Day 84).
Plasma Drug Monitoring	Plasma drug monitoring will be collected on Day 1 and Day 28 pre-dose and post-dose at 0.5 and 1 and 4 hours after the morning dose; on Day 56, a single sample will be collected
Study Eye	If both eyes are affected and meet the inclusion criteria, the eye with the higher overall hyperemia score will be used as the study eye. If both eyes are eligible and have the same hyperemia score, the right eye will be selected as the default study eye

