5.2 Safety Population

The safety population will include all randomized participants who receive at least one (1) dose of study eye drop. Results will be presented based on the treatment actually received. All safety analyses will be conducted using the safety population.

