6.3 Demographic and Baseline/Screening Characteristics

All demographic and baseline data will be summarized per the assigned treatment and overall using the safety population. The following variables will be presented:

- Age (years)
- Age group (18 - 35, 36 - 50, 51 – 65, ≥ 66 yrs)
- Gender (Female, Male)
- Child Bearing Potentials (for females only – No, Yes. If No, Reason - Bilateral oophorectomy; Bilateral tubal ligation; Hysterectomy; Post-menopausal)
- Ethnicity (Hispanic or Latino, Not Hispanic or Latino)

- Race (American Indian or Alaska Native; Asian; Australian Aboriginal or Torres Strait Islander; Black; Native Hawaiian or Other Pacific Islander; White. If Other, list of specified.)
- Iris Color (Black; Blue; Brown; Green; Grey; Hazel; Other. If Other, list of specified.)

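### The protocol's safety population requires a post-baseline visit and the SAP's does not; the two definitions should be made one, including everyone dosed

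*Protocol*

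**What the plan says.** Protocol 9.3 restricts safety analyses to randomized participants who "received at least 1 dose of study drug and attended a post-baseline visit". Protocol 9.4.4 adds: "All safety analyses will be conducted on the safety population using the following safety variables".

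SAP 5.2 states: "The safety population will include all randomized participants who receive at least one (1) dose of study eye drop". It sets no visit condition, and goes on: "All safety analyses will be conducted using the safety population". SAP 6.6 repeats that commitment. SAP 6.3 uses the same set for baseline tables: "All demographic and baseline data will be summarized per the assigned treatment and overall using the safety population".

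Both documents present safety results by treatment received. The only difference in membership is the attendance condition.

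The visit schedule bears on how many people that condition could touch. The footnote to protocol 1.3 says that "Study Visit 2 (V2D7) is a phone call follow-up but may be conducted as an optional in-clinic visit", at the site's discretion. The next scheduled visit is Day 28.

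**The concern.** A safety set normally contains everyone exposed. The protocol's set adds a condition that is met only after exposure, namely coming back. Returning can depend on how well the drop was tolerated, so the condition can select on the outcome that the analysis is meant to measure.

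The design makes this more than a formality. Protocol 6.1.2 and 8.3.7 keep participants in the clinic for at least an hour after the first dose and then ask about AEs. Protocol 8.2 says that immediate effects of the drops are captured through AE reporting. All of this happens on Day 1, before any post-baseline visit. A participant who reacts to the first drop and does not return has a recorded event, but is not in the protocol's safety set.

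Safety and tolerability is the first objective listed in the synopsis, and protocol 2.2 describes this as the first clinical study of topical AG-86893. The comparison of AE incidence with vehicle is one of the two study hypotheses in protocol 4.1, and it rests on this denominator.

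**Working it through.** The plan gives no safety figure to reproduce. The check is a comparison of texts, followed by arithmetic on assumed counts.

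**1. Who differs between the sets**

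| Participant | Protocol 9.3 | SAP 5.2 |
|---|---|---|
| Dosed, attends any clinic visit after Day 1 (optional Day 7, unscheduled, exit, Day 28 or later) | in | in |
| Dosed, Day 7 phone call only | undefined | in |
| Dosed, no contact after Day 1 | out | in |
| Randomized, never dosed | out | out |

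The second row is open because the schedule labels Day 7 a study visit and includes AE review in it, while protocol 9.3 asks for attendance and does not say whether a call qualifies. If it does not, anyone who leaves before Day 28 without a clinic visit falls outside the protocol's set.

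**2. Does any text reconcile the two?** Protocol 9.4.1 calls for a detailed SAP to be approved before lock. SAP 1 says that the SAP is to be read together with the latest protocol. Neither gives an order of precedence. SAP 1.1 does not mention the safety population.

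**3. Inputs for the arithmetic**
- Enrolment of about 70, for 60 evaluable (protocol 9.2, SAP 3.3).
- Allocation 1:1:1, so 70 / 3 = 23.3, or about 23 per arm.
- k, the number of dosed participants with no post-baseline visit, is not given and is assumed below.

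**4. Overall denominator.** With all 70 dosed, the SAP denominator is 70 and the protocol denominator is 70 − k:
- k = 0: 70 (100%)
- k = 1: 69 (98.6%)
- k = 3: 67 (95.7%)
- k = 5: 65 (92.9%)
- k = 10: 60 (85.7%)

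The last line is a loose ceiling. The planned allowance is 70 − 60 = 10, or 10/70 = 14.3%, but it covers drop-out from evaluable status for any reason.

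**5. AE rate in one arm.** Take n = 23 dosed, a participants with an AE among those who return, and k who never return and each had an AE. The SAP rate is (a + k)/n. The protocol rate is a/(n − k).

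| a | k | SAP 5.2 | Protocol 9.3 |
|---|---|---|---|
| 0 | 1 | 1/23 = 4.3% | 0/22 = 0% |
| 3 | 1 | 4/23 = 17.4% | 3/22 = 13.6% |
| 3 | 2 | 5/23 = 21.7% | 3/21 = 14.3% |
| 3 | 3 | 6/23 = 26.1% | 3/20 = 15.0% |

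One such participant therefore moves the rate by 4.3 points (a = 0) or 17.4 − 13.6 = 3.8 points (a = 3), which is about 4 either way.

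If the one who does not return had no AE, the shift is small and in the other direction: 3/23 = 13.0% under the SAP against 3/22 = 13.6% under the protocol. The bias of concern needs non-return to be linked to an event.

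**The case against.** The strongest reply is that the document that specifies the tables already has the better definition. SAP 5.2 includes everyone dosed, SAP 6.6 commits all safety analyses to that set, and protocol 9.4.1 provides for the SAP to carry the detail. Harm arises only if the protocol's sentence is taken to override it. This stands and limits the weight of the point, but it does not settle which text governs.

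Four stronger readings are tempting, and the documents do not support them.

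- **Everyone who stops early is lost.** Protocol 7.1 makes stopping drug an early exit, but an early leaver who attends any exit or unscheduled clinic visit is in both sets. Protocol 7.2 asks for exit procedures at the last visit attended, 7.3 requires contact attempts after a missed visit, and 8.2 allows unscheduled visits. None of these guarantees a return after Day 1, so the gap is narrow but not closed.
- **AE rates would be understated by a third.** That is the k = 2 row above (21.7% against 14.3%) and rests wholly on assumed counts. Nothing in the documents gives the number who never return. In the experience reported in protocol 2.2, 10 + 7 = 17 of 24 dosed had reached at least Day 28, and the two AEs judged possibly related or related began 5 and 14 days into treatment and were followed to resolution.
- **SAP 1.1 conceals a change.** Its heading suggests a list of departures, but its text refers to the amendments in protocol version 3.0 and introduces an extract of them: "The following content are those may affect statistical analysis plan". The safety population was not among those amendments, so its absence from the table shows little.
- **The set could be picked after results are seen.** SAP 8 fixes eligibility for analysis before each database lock. What remains is narrow: SAP 3.4 has Day 28 safety results shown by unmasked group after the first lock, and eligibility is determined again before the final one.

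It is also fair to say that an excluded participant's event would not vanish. Protocol 9.4.8 provides line listings for each participant, and protocol 8.3.9 requires SAE reporting within 24 hours. Only the summary rates by arm would miss it.

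**Conclusion.** The contradiction is real and should be removed. Protocol 9.3 and SAP 5.2 define the set used for all safety analyses differently, and no rule says which applies. The protocol's version is the weaker one, because it makes membership depend on returning after exposure.

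The practical size is unknown and may be nil. It depends on two things that the documents do not settle: how many dosed participants have no post-baseline visit, and whether a Day 7 call counts as one. With about 23 per arm, each affected participant who had an AE changes that arm's rate by about 4 percentage points, enough to be visible in a study of this size. Efficacy results are not affected, because the modified intent-to-treat population is defined separately and in the same terms in both documents.

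**What to change.** In protocol 9.3, delete the condition on attending a post-baseline visit. The safety population then reads as in SAP 5.2: all randomized participants with at least one dose, presented by treatment received. This also removes the need to decide whether a Day 7 call counts as attendance.

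Until the protocol is amended, add a statement to the SAP before the first database lock that its safety population departs from protocol 9.3 and that the SAP 5.2 definition governs.

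The cost is one clause in the protocol and one statement in the SAP. No new data, visits or participants are needed.

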3.1.4 Safety and Other Measures

a) Vital Sign and Laboratory Findings

Vital signs as listed below will be performed at all visits.

- Temperature ((Celsius)
- Respiratory Rate
- Systolic Blood Pressure
- Diastolic Blood Pressure
- Heart Rate
- Height (cm)
- Weight (kg)
- Body Mass Index (kg/m²)

Blood and urine samples will be collected for lab tests at Screening, Day 28, Day 84 or Early Discontinuation, and Unscheduled visits for the following tests:

- Urinalysis
- Hematology
- Serum chemistry

b) Physical Characteristics

c) Pregnancy Testing (for child-bearing participants)

d) Electrocardiogram (ECG) Findings

ECG will be performed at Screening, Day 1, Day 28, Day 84 or Early Discontinuation, and Unscheduled visits. Findings will be recorded as Abnormal or Normal.

e) Best-corrected Visual Acuity (BCVA)

BCVA using the Early Treatment Diabetic Retinopathy Study (ETDRS) visual acuity protocol will be assessed for both eyes at all scheduled visits. The number of letters read correctly will be recorded for both eyes.

f) Intraocular Pressure (IOP)

IOP (mmHg) will be measured using Goldmann applanation tonometer for both eyes at all scheduled visits.

g) Tear Film Break-up Time (TFBUT)

TFBUT (seconds) will be performed for the study eye first, then the other eye at Day 1, Day 28, Day 56, Day 84 (only if abnormal findings on Day 56) and Early Discontinuation visits.

h) Lissamine Green Conjunctival Staining

Conjunctival staining will be performed for the study eye first, then the other eye at Day 1, Day 28, Day 56, Day 84 (only if abnormal findings on Day 56) and Early Discontinuation visits using the following grading:

- 0 = None
- 1 = Mild
- 2 = Moderate
- 3 = Severe.

i) Biomicroscopy

Slit-lamp biomicroscopy examination for both eyes will be performed at all visits for following measurements:

- Eyelids (Abnormal, Normal. If Abnormal, specify)
- Conjunctiva (0 = None, 0.5 = Trace, 1 = Mild, 2 = Moderate, and 3 = Severe)
- Cornea (0 = None, 0.5 = Trace, 1 = Mild, 2 = Moderate, and 3 = Severe)
- Iris (0 = None, 0.5 = Trace, 1 = Mild, 2 = Moderate, and 3 = Severe)
- Lens Status (Clear, Opacity, Pseudophakic, Aphakic)
If Opacity:
 - Nuclear Cataract Grade (: <1, 1, 1.5, 2, 2.5, 3, >3)
 - Posterior Subcapsular Cataract Grade (: <1, 1, 1.5, 2, 2.5, 3, >3)
 - Cortical Cataract Grade (: <1, 1, 1.5, 2, 2.5, 3, >3)

j) Ophthalmoscopy Findings

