Dilated fundus examination will be performed for both eyes at Screening, Day 1, Day 28, Day 84 or Early Discontinuation, Unscheduled visits for the following assessments:

- Vitreous (Abnormal (CS), Abnormal (NCS), Normal. If Abnormal, specify)
- Macula (Abnormal (CS), Abnormal (NCS), Normal. If Abnormal, specify)
- Optic Nerve (Abnormal (CS), Abnormal (NCS), Normal. If Abnormal, specify)
- Peripheral Retina (Abnormal (CS), Abnormal (NCS), Normal. If Abnormal, specify)

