6.5.2 Secondary and Exploratory Variables and Sub-Study Variables

Secondary, exploratory and exploratory sub-study numerical endpoints will be explored using the same approach as outlined for the primary efficacy analysis and might include the following:

- Change from baseline in conjunctival hyperemia score at the study quadrant at Days 28
- Change from baseline in pterygium vascularity at Days 28 and 56

- Change from baseline in pterygium vessel length at Days 28 and 56
- Change from baseline in Pterygium volume at Days 28 and 56
- IOP
- BCVA in letters read correctly
- Biomicroscopy parameters for conjunctiva, cornea, and iris. Lens status scale
- TFBUT
- Lissamine green conjunctival staining score
- Fundus
- Participant questionnaire

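### Fundus findings, and possibly lens status, are recorded as named categories, but the only inferential method named for them is a linear model on means, so the result depends on a coding that the plan never gives

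*Protocol*

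**What the plan says.** **Method.** Protocol 9.3 gives a general rule: "Nominal data will be analyzed using the Pearson chi-square test or Fisher exact test". Its next sentence names specific variables for a different method: "BCVA, ophthalmoscopy, AS-OCT, and IOP data will be analyzed using analysis of variance models with dose strength as main effects". SAP 6.5.2 says that secondary, exploratory and sub-study "numerical endpoints will be explored using the same approach as outlined for the primary efficacy analysis and might include the following". The list that follows includes fundus and this line: "Biomicroscopy parameters for conjunctiva, cornea, and iris. Lens status scale". The primary approach (SAP 6.5 and Appendix 2) is a mixed model reporting least-squares means with Bonferroni adjustment.

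**Data.** SAP 3.1.4 records the dilated fundus examination separately for vitreous, macula, optic nerve and peripheral retina, for example "Macula (Abnormal (CS), Abnormal (NCS), Normal. If Abnormal, specify". Lens status is recorded as "Lens Status (Clear, Opacity, Pseudophakic, Aphakic". If there is opacity, ordered grades are added, for example "Nuclear Cataract Grade (: <1, 1, 1.5, 2, 2.5, 3, >3". The plan gives no numeric code for the fundus or lens-status categories, and no rule for combining the four fundus structures.

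**Other displays.** SAP 6.6.2 gives the number and percent of participants with abnormal fundus findings by group at each visit. Protocol 8.2 requires clinically significant findings to be recorded as adverse events, and SAP 6.6.1 tabulates adverse events by arm.

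**The concern.** Change in ophthalmoscopy findings is a named safety endpoint (protocol synopsis and section 3) in the first clinical study of the topical product (protocol 2.2). A programmer cannot run an analysis of variance on Normal / NCS / CS without inventing scores, and the two documents supply none. Whatever scores are chosen, the between-arm difference has no clinical unit. Non-significant findings in one arm can offset clinically significant ones in another, and a different coding gives a different p-value.

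The by-group count in SAP 6.6.2 does not cure this. It treats NCS and CS alike, does not count change from baseline, and plans no comparison. SAP Appendix 2 holds Miettinen-Nurminen risk-difference code, but no endpoint is assigned to it.

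**Working it through.** **The plan's own figure.** The plan gives no figure for ophthalmoscopy, fundus or lens status. Its one power statement (protocol 9.2: at least 90%, 20 per arm, SD 1.0, difference 1) concerns hyperemia. It reproduces as 0.8997 for an overall F test with one arm differing by 1, and nothing below depends on it.

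**Inputs.** The categories come from SAP 3.1.4. Arm size is 20 evaluable, or about 23 enrolled (70/3 = 23.3), from protocol 9.2. All counts below are assumed for illustration and were chosen to show cancellation; they are not trial data or a forecast.

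**Illustration A: 20 per arm, Normal/NCS/CS.** Vehicle 14/6/0; 0.1% 14/6/0; 0.3% 17/0/3.

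| Coding (Normal, NCS, CS) | Means: vehicle, 0.1%, 0.3% | ANOVA p |
|---|---|---|
| 0, 1, 2 | 0.30, 0.30, 0.30 | 1.00 |
| 0, 1, 3 | 0.30, 0.30, 0.45 | 0.76 |
| 1, 0, 2 | 0.70, 0.70, 1.15 | 0.002 |

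The Fisher-Freeman-Halton test on the same 3×3 table gives p of about 0.006 (simulated). The third coding puts the categories out of clinical order. It shows what an unspecified coding allows, not what a careful analyst would choose. The SAP 6.6.2 display would show 30%, 30% and 15% abnormal, which points in favour of 0.3%. CS alone is 3/20 against 0/20, Fisher p = 0.23.

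**Illustration B: 23 per arm.** Vehicle 17/6/0; 0.1% 19/4/0; 0.3% 20/0/3, coded 0/1/2.

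- Means: 6/23 = 0.26; 4/23 = 0.17; (3×2)/23 = 0.26.
- Within-arm sum of squares, Σx² − (Σx)²/n: (6 − 36/23) + (4 − 16/23) + (12 − 36/23) = 4.43 + 3.30 + 10.43 = 18.17. Mean square = 18.17/66 = 0.275.
- Between-arm sum of squares = 0.116, so F = (0.116/2)/0.275 = 0.21, p = 0.81.
- 0.3% minus vehicle = 0.00. Standard error = √(0.275 × 2/23) = 0.155. The Bonferroni t for three comparisons on 66 df is 2.457, so the interval is ±0.38.
- Scoring CS as 5 or 10 keeps the order and moves p to 0.27 or 0.11.
- SAP 6.6.2 display: 3/23 = 13% abnormal on 0.3% against 6/23 = 26% on vehicle.
- CS only: 3/23 − 0/23 = 13 points, Miettinen-Nurminen 95% CI about −2.5 to 32 points; Fisher p = 0.23.

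**Lens status: 20 per arm, Clear/Opacity/Pseudophakic/Aphakic.** Vehicle 14/2/4/0; active 10/10/0/0. Coded 1 to 4, the means are (14 + 4 + 12)/20 = 1.5 and (10 + 20)/20 = 1.5, p = 1.00. Swapping the codes for opacity and pseudophakia gives 1.4 and 2.0, p = 0.036. Fisher on opacity (2/20 against 10/20) gives p = 0.014. These categories have no natural order, so neither coding is privileged.

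**The case against.** A reader might infer that the linear model is the only between-arm look at posterior-segment harm, and that it could hide such harm. The documents do not support that. SAP 6.6.2 plans by-group counts of abnormal fundus findings. Clinically significant findings become adverse events and appear in the by-arm tables, so three new CS findings on 0.3% would still show as 3/23 against 0/23. A cataract increase of at least two grades is also counted by group as an event of special interest (SAP 4.7.1 and 6.6.1).

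Four further objections carry weight:

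- SAP 6.5.2 is permissive and limited to numerical endpoints, and uncoded categories arguably fall outside it. That softens the SAP but not protocol 9.3, which is a firm statement about ophthalmoscopy.
- Normal / NCS / CS can be read as ordered. That is fair, but order does not supply spacing: in illustration B the p-value moves from 0.81 to 0.11 with the order kept.
- The lens status scale may mean the ordered cataract grades, since protocol 8.2 assesses the lens on the Age-Related Eye Disease Study scale. The text does not settle this. Lens status is also not a posterior-segment measure.
- The counts are constructed and use raw codes rather than change from baseline, and Fisher gives only p = 0.23 on the CS findings. The remedy therefore would not declare a difference there either. In an exploratory trial of this size, descriptive counts are a defensible main display for rare findings.

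What stands is that a named analysis does not suit the recorded data and conflicts with the protocol's own rule for nominal data.

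**Conclusion.** The point holds in a limited form. The linear model is the only inferential method named specifically for fundus, and it cannot be run on the recorded categories without a coding that neither document gives. Its result is coding-dependent: p runs from 1.00 to 0.002 on one set of assumed counts, the low end needing an out-of-order coding, and from 0.81 to 0.11 on another with the order kept. It can show no difference where the category distributions differ. For lens status the point is conditional on the term meaning the four categories.

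The sizes rest entirely on illustrative counts and show what could happen, not how likely it is. The adverse event tables are a real backstop for new clinically significant findings. The remaining gap is that the planned fundus count merges CS with NCS and does not count change from baseline. This affects a safety display and not the primary efficacy conclusion, but it is a stated wrong method for a named safety endpoint and should be corrected.

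**What to change.** 1. Protocol 9.3: delete ophthalmoscopy from the analysis-of-variance sentence, so that the nominal-data rule governs it.
2. SAP 6.5.2: delete fundus and the four-category lens status. If the lens status scale means the cataract grades, say so and analyse the change in grade as ordinal.
3. SAP 6.6.2: in the safety population, tabulate by arm the participants whose study eye has a new or worsened fundus finding since baseline (Normal to Abnormal, or NCS to CS), with CS shown separately from NCS. For lens status, count a change of category.
4. For each dose minus vehicle, give the risk difference with a Miettinen-Nurminen 95% CI, using the code already in SAP Appendix 2, and a Fisher exact test under the protocol's rule.

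The cost is short wording changes in two documents and one small table; no new data are needed. The intervals will be wide at about 20 to 23 per arm, so the change gives an interpretable estimate and not power. Counts and listings remain the main evidence for rare findings.
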